7.3.1.3 ANOVA Models and Logistic regression for Baseline Biomarker Values

Baseline values are defined as the last measurement taken by the end of Visit 2.

To compare baseline biomarkers and clinical assessments across subject groups, analysis of covariance (ANOVA) models for continuous variables and logistic regressions for ordinal and categorical variables will be conducted. Demographic variables and baseline disease status are adjusted to account for potential imbalance in baseline values. A detailed list of covariates will be discussed in TSAP.

7.3.1.4 Predictive models

To examine the predictive potential of the biomarkers—soluble, imaging and physiological—in clinical outcomes, e.g. FEV₁ decline at week 56, separate regression models are fitted for the clinical assessments using changes from baseline at each post-baseline time-point while adjusting for baseline covariates.

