Name of company:	Boehringer Ingelheim		
Name of finished product:			
n/a			
Name of active ingredient:			
n/a			
Protocol date: 02 Sep 2015	Study number: 352.2069		Revision date: 24 Feb 2020
Main criteria for inclusion:	
• COPD and healthy subjects of both sex aged ≥ 40 and ≤ 70 years• COPD with A1ATD of both sex aged ≥ 30 and ≤ 70 years• COPD and healthy ex-smokers with a smoking history ≥ 20 pack years• COPD with A1ATD ex-smokers with a smoking history ≥ 10 pack years• Body mass index (BMI) of ≥ 18 and ≤ 35 kg/m^2 (≤ 30 kg/m^2 in the MRI substudy)		
Duration of observation:	156 weeks (~ 3 years)		
Assessments:	
Clinical assessments:
 
• Spirometry• Body plethysmography• Pulse oximetry• Diffusing capacity of the lung for carbon monoxide• Questionnaires: mMRC, CAT, SGRQ• BODE index• 6 minute walk test (6 MWT)• Medical Events of Special Interest (MESI)• Adverse Events 
Biofluids:
 
• Blood• Induced Sputum (at selected sites) 
Imaging assessments:
 
• Chest CT (inspiratory/expiratory)• Magnetic Resonance Imaging (MRI) (in a subset of healthy subjects and patients with COPD without A1ATD)		
Biobanking:	Unspecified biomarker testing in blood in all subjects and sputum in a subset of subjects		
Safety criteria:	Vital signs, physical examination, safety laboratory, urine pregnancy testing, 12-lead electrocardiogram (ECG) and adverse event reporting		
Statistical methods:	Descriptive statistics, Pearson and rank-based correlation, multivariate statistical prediction model		

FLOWCHART

Study Periods	Screening Period	Observational Period									
		1	2	3	4	5	6	7	8	9	10
Visit		1									
Weeks			12	26	39	52	65	78	91	104	
Days	Prior to any study related procedure	-28 to -1	1	84	182	273	364	455	546	637	728
Time window for visits			see ¹⁷	± 7d	± 14d	± 14d	± 14d	± 14d	± 14d	± 14d	± 14d
Informed consent ¹	X										
Demographics	X										
Medical history	X										
Physical examination, BMI ¹⁰	X						X				X
Vital signs	X						X				X
Review of in-/exclusion criteria	X	X ¹²									
MESI Check	X	X	X	X	X	X	X	X	X	X	X
Smoking Status/Cotinine Test ¹⁸	X	X	X	X			X				X
Restrictions Check ⁸	X	X		X			X				X
Urine pregnancy test ²	X	X		X			X				X
Safety laboratory ^{3,5}	X	X	X	X			X				X
A1ATD testing ¹⁴	X										
12 lead-ECG	X						X				X
BODE index ¹⁵		X									X
mMRC ⁴	X	X					X				X
CAT ⁴		X					X				X
SGRQ ⁴		X					X				X

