Pulse oximetry	X	X		X			X				X
Spirometry (PFT) ¹⁹	X	X	see ²¹	X			X				X
Lung diffusion capacity ²⁰	X	X		X			X				X
Body plethysmography ²⁰		X		X			X				X
Chest CT		X					X				X
MRI (in a substudy only) ⁷		X		X			X				X
Induced sputum ¹⁶		X	X	X			X				X
6 minute walk test (6 MWT)		X ¹¹	X								X
BM blood collection ⁵		X	X	X			X				X
DNA banking (optional) ⁹		X									
Re-/Dispense and review subject reminder diary ¹³		X	X	X	X	X ²²	X	X ²²	X ²²	X ²²	X
Adverse events		X	X	X	X	X	X	X	X	X	X
Concomitant therapy		X	X	X	X	X	X	X	X	X	X
IRT subject visit registration		X	X	X	X	X	X	X	X	X	X
Completion of subject participation											
Vital status and COPD exacerbation status collection ⁶							X				X

FLOWCHART (continued)

Study Periods	Observational Period			
Visit				7
Weeks	117	130	143	156
Days	819	910	1001	1092
Time window for visits	± 14d	± 14d	± 14d	± 14d
Informed consent ¹				
Demographics				
Medical history				
Physical examination, BMI ¹⁰				X
Vital signs				X
Review of in-/exclusion criteria				
MESI Check	X	X	X	X
Smoking Status/Cotinine Test ¹⁸				X
Restrictions Check ⁸				X
Urine pregnancy test ²				X
Safety laboratory ^{3,5}				X
A1 ATD testing ¹⁴				
12 lead-ECG				X
BODE index ¹⁵				X
mMRC ⁴				X
CAT ⁴				X
SGRQ ⁴				X
Pulse oximetry				X
Spirometry (PFT) ¹⁹				X
Lung diffusion capacity ²⁰				X
Body plethysmography ²⁰				X
Chest CT				X
MRI (in a substudy only) ⁷				X
Induced sputum ¹⁶				X
6 minute walk test (6 MWT)				X
BM blood collection ⁵				X
DNA banking (optional) ⁹				
Re-/Dispense and review subject reminder diary ¹³	X ²²	X ²²	X ²²	X
Adverse events	X	X	X	X
Concomitant therapy	X	X	X	X
IRT subject visit registration	X	X	X	X
Completion of subject participation				X
Vital status and COPD exacerbation status collection ⁶				X

Proprietary confidential information © 2020 Boehringer Ingelheim International GmbH or one or more of its affiliated companies

- 1 All subjects must sign an informed consent consistent with ICH-GCP guidelines prior to participation in the study, which includes the application of medication short-term restrictions prior to lung function testing. Re-consenting may become necessary when new relevant information becomes available and should be conducted according to the sponsor's instructions
- 2 Urine pregnancy testing in women of childbearing potential only (to be assessed prior to blood collection and imaging assessments)

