2. RATIONALE, OBJECTIVES, AND BENEFIT - RISK ASSESSMENT

2.1 RATIONALE FOR PERFORMING THE STUDY

Pharmacological treatment of COPD is currently based on bronchodilators and anti-inflammatory drugs. Approved medicines may relieve symptoms, reduce exacerbations and/or improve health status and exercise tolerance, but there is no treatment for disease progression in COPD, and systematic treatment options, apart from smoking cessation, do not prevent rate of decline of FEV₁ over time, nor inhibit the lung structural damages.

More in depth understanding of COPD patient phenotypes and the course and drivers of COPD disease progression is required to address this unmet medical need and enable drug development aiming at a reduction of COPD disease progression.

Biomarkers may assist, beside clinical parameters, in characterizing patients and potentially in predicting and monitoring their disease course.

[REDACTED]

increase the understanding of the underlying pathophysiology of emphysema progression.

BI plans to conduct this longitudinal emphysema progression biomarker study to identify biomarkers (soluble, functional imaging and physiological) that may be useful in differentiating a patient population with ongoing emphysematous destruction of lung parenchyma, which may enable development of drugs aiming at the reduction of COPD progression.

Rationale for the study extension to 3 years

It has become known from consortia data (████████) that lung density decline, as assessed by CT and lung function decline, do not correlate across GOLD stages [R18-1744]. Therefore, besides characterizing emphysema progression in patients it will be important to also assess lung function decline by spirometry since this describes an additional high risk COPD patient subgroup with a large unmet medical need. Since detection of lung function decline is expected to take longer (3 years) than detection of lung density decline, the study is being extended to a 3 year observation time.

This study will include 60 healthy subjects (ex-smokers without airflow limitation), 125 COPD GOLD 1, 125 COPD GOLD 2, 125 COPD GOLD 3, and up to 20 patients with COPD and A1AT deficiency (ZZ genotype). Soluble and imaging biomarkers will be investigated addressing different aspects of disease pathways postulated to be relevant for COPD

2.2

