5.1 PRIMARY ENDPOINT(S)

The main outcome measures of the study are described in CSP Section 5.1.1. To clarify the CSP wording, the main outcomes are also listed here:

- Absolute change from baseline in lung density based on PD15 adjusted for lung volume (ALD) [g/L/year] (up to week 156) (for definition of ALD see Section 9.2)
- Annual rate of lung function decline based on FEV1 [mL/year] (up to week 156)
- Number of exacerbations during study (up to week 156)
- Duration of exacerbations during study [days] (up to week 156)
- Occurrence of an at least moderate exacerbation during study (up to week 156)
- Occurrence of a severe exacerbation during study (up to week 156)

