7.4 PRIMARY ENDPOINT(S)

7.4.1 Primary analysis

Primary analysis will be performed on per protocol set – biomarker subjects (PPSBM).

Absolute change in lung density decline based on PD15 adjusted for lung volume (ALD) [g/L/year] (up to week 156)

The change from baseline over time for PD15 adjusted for lung volume (ALD) will be evaluated with a restricted maximum likelihood (REML) based mixed model for repeated measures (MMRM) approach with the fixed, categorical effects of subject groups (SG) at each visit. Visit (weeks) will be treated as the repeated measure with an unstructured covariance structure used to model the within-patient measurements.

The statistical model will be as follows:

$$y_{ijk} = \tau_{jk} + e_{ik} , e_{ik} \sim N(0, \sigma^2)$$

[figure not shown]
 y_{ijk} = change from baseline for ALD for subject i in subject-group (SG) j at visit k, k = 5, 6, 7

 τ_{jk} = the fixed effect subject-group (SG) j at visit k, j=0,...,4

The subject-group indicator is defined as:

$$SG = \begin{cases} 0, & \text{Ex} - \text{smoking control (reference category)} \\ 1, & \text{COPD GOLD 1} \\ 2, & \text{COPD GOLD 2} \\ 3, & \text{COPD GOLD 3} \\ 4, & \text{COPD} + \text{A1ATD} \end{cases}$$

The Kenward-Roger approximation will be used to estimate denominator degrees of freedom and adjust standard errors. Significance tests will be based on least-squares means using a two-sided $\alpha = 0.05$ (two-sided 95% confidence intervals).

Annual rate of lung function decline based on FEV1 [L/year] (up to week 156)

The continuous outcome measure FEV1 [L] will be analysed by performing a restricted maximum likelihood (REML) based approach using a random slope and intercept model. The analysis will include the fixed, categorical effect of subject-group indicator (SG, as specified above), and the fixed continuous effects of 'time' as well as the SG-by-time interactions. Random effects will be included for patient response for both time and intercept.

The statistical model will be as follows:

$$y_{ijk} = (a + a_i + \tau_j) + (\gamma + g_i + \varphi_j)t_{ik} + e_{ik} ,$$

$$iid$$

$$(a_i, g_i) \sim N_2(\mathbf{0}, \mathbf{\Sigma}), e_{ik} \sim N(0, \sigma^2)$$

 y_{ijk} = response variable (FEV1 [L]) for subject i in at visit k belonging to SG j,

 α = mean patient intercept

 a_i = random intercept effect for subject i, i=1,2,...

 τ_i = intercept coefficient of the effect of subject-group j, j=0, 1, 2, 3, 4

 γ = mean patient slope

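### For FEV1, Protocol 7.3.1.4 predicts visit-by-visit change with no leading outcome, while the SAP's main outcome is the annual slope to Week 156, and its one example names an unscheduled week

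*Protocol*

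**What the plan says.** Protocol 7.3.1.4 (Predictive models) names one outcome, introduced as an example, and then gives the form of the models: FEV1 "decline at week 56, separate regression models are fitted for the clinical assessments using changes from baseline at each post-baseline time-point", with adjustment for baseline covariates.

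The protocol flowchart lists contacts after Visit 2 at Weeks "12 26 39 52 65 78 91 104" and then "117 130 143 156". Scheduled post-baseline spirometry is at Weeks 26, 52, 104 and 156. FEV1 at Week 12 is a safety check for sputum induction.

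Protocol 2.1 gives the reason for the third year: "Since detection of lung function decline is expected to take longer (3 years) than detection of lung density decline".

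SAP 5.1 lists as a main outcome "Annual rate of lung function decline based on FEV1 [mL/year] (up to week 156". SAP 7.4.1 estimates it "using a random slope and intercept model". The terms are subject group, time and their interaction, and there is no biomarker term. SAP 4.2 declares no change to the analyses planned in the protocol, so 7.3.1.4 stands as written.

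**The concern.** The study exists to find biomarkers related to progression over 156 weeks. The visible text leaves open which FEV1 quantity they are to predict. The main outcome is a slope over all visits. The prediction target is a set of separate changes from baseline, all with equal standing, and the single example does not identify a real visit.

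Two things are at stake. First, change over a short interval is mostly visit-to-visit variation when annual decline is small. A real association would then look weak at the early visits, and a null result there would say little about the biomarker. Second, each per-visit model uses a different set of subjects. A Week 156 change model loses everyone without a Week 156 value. That includes subjects who did not consent to year 3 (SAP 7 displays them as completers at Week 104) and those whose data at that visit are removed under SAP 6.6.3, where nothing is imputed.

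**Working it through.** **The plan's own figure.** Protocol 7.7.3 gives power 0.805 for a partial correlation of 0.30 with n = 100, 15 covariates and two-sided alpha 0.05. By Fisher's z with m = 100 − 15 = 85: z = atanh(0.30) + 0.30/(2 × 84) = 0.3113; 0.3113 × √82 = 2.819; 2.819 − 1.960 = 0.859; Φ(0.859) = 0.805. It reproduces, and it does not depend on Week 56.

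**Schedule.** Week 56 is day 56 × 7 = 392. The Week 52 visit window is days 350 to 378 (SAP Table 6.7: 1), so day 392 is 14 days past it. It falls inside the SAP analysis window for Week 52 (days 274 to 546), so a measurement there would be reported as Week 52.

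**Inputs for the information content of each outcome.**
- True between-subject slope SD, b: 40 mL/year. Protocol 7.7.1 reports SDs of annual decline from about 20 to over 60; range used 20 to 60.
- Within-subject visit SD, s: 100 mL. This is an assumption, not in the documents; range used 60 to 150.
- Spirometry times: 0, 0.5, 1, 2 and 3 years. Mean 1.3; Sxx = 1.69 + 0.64 + 0.09 + 0.49 + 2.89 = 5.8.
- Linear individual decline and independent visit errors.

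**Formulas.** Share of variance that is true decline:
- change over T years: b²T² / (b²T² + 2s²)
- least-squares slope: b² / (b² + s²/Sxx)

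An observed correlation is the true one times the square root of this share. As an illustration, the true biomarker–slope correlation is set to the protocol's 0.30, with n = 100 and 15 covariates.

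| FEV1 outcome | Share of true decline | Multiplier | Observed r | Power |
|---|---|---|---|---|
| Week 26 change | 400/20,400 = 0.020 | 0.14 | 0.04 | 7% |
| Week 52 change | 1,600/21,600 = 0.074 | 0.27 | 0.08 | 12% |
| Week 104 change | 6,400/26,400 = 0.242 | 0.49 | 0.15 | 27% |
| Week 156 change | 14,400/34,400 = 0.419 | 0.65 | 0.19 | 43% |
| Slope, all visits | 1,600/(1,600 + 1,724) = 0.481 | 0.69 | 0.21 | 49% |

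**Range.** Over b = 20 to 60 and s = 60 to 150, power is 6% to 36% for one-year change, 12% to 72% for three-year change and 13% to 74% for the slope. In every combination the order is one-year change, three-year change, slope.

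**Subjects who stop at Week 104.** Their times are 0, 0.5, 1 and 2 years: mean 0.875, Sxx = 0.766 + 0.141 + 0.016 + 1.266 = 2.19. The share for such a slope is 1,600/(1,600 + 10,000/2.19) = 0.26. The slope model keeps that information; a Week 156 change model discards it.

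**The case against.** The strongest objection is that the operative analysis cannot be seen. The public SAP goes from 7.5.2 to 7.7, and its history table says the multivariate analysis was defined in more detail in the final version. A model linking biomarkers to the FEV1 slope may be there. This stands. A reader might infer that the plan contains no such model, but the documents support only the statement that none is visible.

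A reader might also infer that prediction is confined to about one year, or that the main FEV1 outcome is set at a visit that does not exist. Neither follows. Week 56 is only an example, the models are fitted at every post-baseline time-point including Weeks 104 and 156, and the main FEV1 analysis runs to Week 156. Nor can Week 56 be read as a misprint for a particular visit: nothing shows whether Week 52, Week 156 or another was intended.

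Per-visit change has legitimate uses. The CT density outcome is itself analysed as change from baseline by visit, and the interim analyses rest on 52- and 104-week data. Protocol 5.1.1 speaks of lung function decline over the course of the study, which Week 156 change would satisfy. Protocol 2.1 makes a comparison with density decline and does not call the early FEV1 models uninformative. The point is therefore confined to FEV1 and to which analysis should lead.

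Protocol 7.3.1.5 and 7.3.2 plan repeated-measures models and further prediction models, but the first describes time profiles and the second does not define the outcome, so they do not settle the question.

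Finally, the visit SD is assumed, and the protocol's SDs may already contain measurement error. That would change the absolute figures but not the ranking.

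**Conclusion.** The point holds for FEV1 as a mismatch between the prediction target in Protocol 7.3.1.4 and the outcome in SAP 5.1 and 7.4.1, together with an example that matches no scheduled visit. At b = 40 and s = 100, early change is a weak target: about 7% true decline at Week 52, against 42% at Week 156 and 48% for the slope. With complete data, the slope's advantage over Week 156 change is modest (multiplier 0.69 against 0.65). Its further merit is that it keeps subjects with no Week 156 value; how many there will be cannot be calculated from the documents.

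Protocol 7.2 makes every test exploratory, so no confirmatory error rate is affected. The issue is how clearly and efficiently the study's central question is answered. It should be corrected, with medium confidence because part of the SAP is not visible.

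**What to change.** For FEV1, name the SAP 7.4.1 random-slope model, with baseline biomarker and biomarker-by-time terms added and all visits to Week 156 used, as the lead predictive analysis. The biomarker-by-time coefficient then measures how the annual rate of decline differs with the biomarker. Keep the per-visit change regressions as supportive and say so in 7.3.1.4. Replace Week 56 with a scheduled visit; the sponsor must state which was meant. If the non-visible multivariate section already predicts the FEV1 slope, align the protocol wording with it and change nothing else.

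The cost is wording in the protocol and SAP and two terms in a model already specified. No new data are needed. The small downside is the assumption of a linear time trend, which the main FEV1 analysis already makes.

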7.3.1.5 Repeated Measurement Models for Changes in Biomarkers Over Time

Repeated measurement models are fitted for selected biomarkers and clinical assessments. This method provides a time profile and an overall trend for changes in these assessments.

7.3.2 Secondary analyses

Exploratory statistical regression and prediction models will be developed for clinical assessments based on biomarker values alone, and based on biomarker values in conjunction with established baseline covariates. Their performances will be evaluated. Different approaches such as penalized regression models, recursive partitioning, or classification and regression tree (CART) methods will be investigated.

7.3.4 Safety analyses

All subjects enrolled will be included in the safety analysis. In general, safety analyses are descriptive in nature and are based on BI standards. No hypothesis testing is planned. Adverse events (AEs) will be coded using the latest version (at the time of database lock) of Medical Dictionary for Regulatory Activities (MedDRA) coding dictionary. Standard BI summary tables and listings will be produced by subject groups.

Statistical analysis and reporting of AEs will focus on AEs that are study procedure related as judged by the investigators and medical events of special interest (MESI) as defined in [Section 5.7.](#)

Frequency, severity, and causal relationship of AEs will be tabulated by system organ class and preferred term after coding according to the latest version of MedDRA. Frequency of MESIs will be tabulated by disorder.

Laboratory data will be analyzed both quantitatively as well as qualitatively. The latter are done via comparison of laboratory data to their reference ranges. Values outside the reference range as well as values defined as clinically relevant will be highlighted in the listings.

Subject groups will be compared descriptively with regard to distribution parameters as well as with regard to frequency and percentage of patients with abnormal values or clinically relevant abnormal values.

Vital signs, physical examinations, or other safety-relevant data observed at screening, baseline, during the course of the study and at the end-of-study evaluation will be assessed with regard to possible changes compared to findings before start of treatment.

7.3.5 Pharmacokinetic analyses

Not applicable

7.3.6 Pharmacogenomic analyses

Genomic parameters are assessed at baseline only. They may be adjusted in the aforementioned statistical models as baseline covariates.

7.4 INTERIM ANALYSES

An interim analysis will be conducted after data from the 52-week and 104-week assessment are available for at least 70% of subjects entered in the study. An interim database lock will occur. The interim analysis will be conducted by the trial team. Detail of the planned statistical analyses will be defined in the TSAP. No separate CTR will be provided. Results of this analysis will be stored.

7.5 HANDLING OF MISSING DATA

Missing data may be imputed if deemed necessary. Details will be discussed in the Trial Statistical Analysis Plan (TSAP).

7.6 RANDOMISATION

Not applicable.

7.7 DETERMINATION OF SAMPLE SIZE

Due to the exploratory nature of the study, power computations are focused on attaining desired precisions for biomarker estimates and relevant clinical assessments in all COPD patient groups except for the A1ATD group.

Calculations are performed in SAS 9.3 using PROC POWER procedure. By assuming up to a 20% dropout rate, at least 100 subjects are expected to contribute to the analysis at the end of 3-year study period. The computations are thus based on 100 subjects in each COPD patient group.

7.7.1 Power computation based on FEV₁ annual decline

Available information reports standard deviations (SD) of annual FEV₁ decline ranging from about 20 mL/year [[P12-04707](#)] to over 60 mL/year [[R15-3625](#)].

Using this information, with a planned 100 subjects in each group, the following table provides the coverage probability for the half-width of a 95% confidence interval (CI) for the decline of FEV₁ for a given SD. For example, if the observed SD is 50 mL/year, and the true half-width of the CI is 11 mL/year, with 100 subjects, the probability that the observed CI will cover the true CI is 93.8% (see highlighted cells in [Table 7.7.1: 1](#)).

Table 7.7.1: 1 Coverage probability of 95% confidence intervals
(alpha = 0.05, n = 100)

SD	Half-width of a 95% CI									
	6	7	8	9	10	11	12	13	14	15
25	0.998	>.999	>.999	>.999	>.999	>.999	>.999	>.999	>.999	>.999
30	0.557	0.993	>.999	>.999	>.999	>.999	>.999	>.999	>.999	>.999
35	0.026	0.557	0.983	>.999	>.999	>.999	>.999	>.999	>.999	>.999
40	<.001	0.048	0.557	0.97	>.999	>.999	>.999	>.999	>.999	>.999
45	<.001	<.001	0.072	0.557	0.954	>.999	>.999	>.999	>.999	>.999
50	<.001	<.001	0.003	0.097	0.557	0.938	0.998	>.999	>.999	>.999
55	<.001	<.001	<.001	0.006	0.122	0.557	0.921	0.996	>.999	>.999

Table 7.7.1: 1 (cont.) Coverage probability of 95% confidence intervals
 (alpha = 0.05, n = 100)

SD	Half-width of a 95% CI									
	6	7	8	9	10	11	12	13	14	15
60	<.001	<.001	<.001	<.001	0.011	0.146	0.557	0.905	0.993	>.999
65	<.001	<.001	<.001	<.001	<.001	0.018	0.168	0.557	0.889	0.988
70	<.001	<.001	<.001	<.001	<.001	0.001	0.026	0.189	0.557	0.873

[figure not shown]

Figure 7.7.1: Visual presentation of [Table 7.7.1: 1](#)

